1.2.3 Clinical Studies with Bimatoprost SR

Study 192024-041D was a phase 1/2 paired-eye comparison study evaluating the safety and efficacy of 4 dose strengths of Bimatoprost SR (6, 10, 15, or 20 µg [2 x10 µg implants]), as single or repeat administrations in 1 eye (study eye), versus the use of topical LUMIGAN 0.03% once daily in the contralateral eye (nonstudy eye). The objective of this study was to evaluate the safety and IOP-lowering efficacy of Bimatoprost SR in patients with OAG.

A total of 109 patients received at least a single administration of Bimatoprost SR, and 24 patients received a repeat administration of Bimatoprost SR. A trend in dose response was observed across the 4 dose strengths that were tested.

Data suggest that the implant may provide topical prostaglandin analog-like efficacy up to 3 to 4 months post-implantation in the majority of patients. Data following the second administration in the retreated patients showed similar IOP lowering efficacy to that observed following the first administration of Bimatoprost SR. In addition, efficacy was maintained longer than the expected 3- to 4-month duration in many patients in this completed study. By Month 6, most patients (> 66%) were still maintained on monotherapy with the initial Bimatoprost SR implant administered. Among all Generation 2 dose strengths, at least 33% of patients had not received rescue or a second Bimatoprost SR treatment by Month 12. At Month 24, at least 23% of patients had not received rescue or a second treatment.

Bimatoprost SR showed an acceptable safety profile with single and repeat administrations in study 192024-041D. Most adverse events were ocular, mild or moderate in severity, occurred within the first 2 days after Bimatoprost SR administration, and were considered related to the study drug administration procedure. There were no reports of serious study drug-related adverse events, and no new safety concerns were observed after the second treatment. Please refer to the Investigator's Brochure for details on reported safety findings.

Two identical global phase 3 studies (Studies 192024-091 and 192024-092) were initiated in late 2014. These studies are assessing the safety and efficacy of Bimatoprost SR in multicenter, randomized, masked, parallel-group comparison studies of 2 dose strengths of Bimatoprost SR (10 and 15 µg) to an active control (timolol maleate 0.5%).

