4.5.2 Prohibited Medications/Treatments

The decision to administer a prohibited medication/treatment is taken with the safety of the study participant as the primary consideration. When possible, Allergan should be notified before the prohibited medication/treatment is administered.

During the study, patients must not participate in other investigational drug or device studies.

Nonstudy IOP-lowering Treatments

Any concurrent nonstudy IOP-lowering treatment (eg, topical ophthalmic medication containing an ocular antihypertensive, LT) is prohibited in either eye during the study (through Month 24), unless necessary for the safety of the patient due to inadequate control of IOP as determined by the investigator. Inadequate control of IOP should be confirmed at a subsequent visit (scheduled or unscheduled visit). Initiation of treatment in one eye should not automatically lead to initiation of treatment in the contralateral eye. Each eye should be evaluated on an individual basis when determining the need for additional nonstudy IOP-lowering treatments. If nonstudy IOP-lowering treatment is initiated, the investigator will be expected to attest to the need for additional nonstudy IOP-lowering treatment for safety reasons for each eye individually. Use of any concurrent nonstudy IOP-lowering treatment with any known effect on study outcomes (eg, crossover effect on the contralateral eye) is prohibited during the study.

In order to maintain patient masking to treatments assigned to each eye, patients who have received nonstudy topical IOP-lowering treatment in a Bimatoprost SR eye will receive Sham Bimatoprost SR administration in that eye on the Bimatoprost SR Cycle 2 administration day(s). If nonstudy topical IOP-lowering medication is initiated in an SLT eye, the patient will continue to receive Sham Bimatoprost SR administration in the SLT eye on the administration day(s). In all cases, the contralateral eye that does not require nonstudy topical IOP-lowering medication will maintain the same treatment regimen assigned at randomization. Patients who have received nonstudy IOP-lowering treatment in both eyes will not receive Bimatoprost SR administration or Sham Bimatoprost SR administration in either eye, and therefore do not need to attend the Bimatoprost SR (or Sham Bimatoprost SR) administration visits and immediate postadministration visits (ie, Bimatoprost SR Cycle 2

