5.9.1.5 Retreatment with Bimatoprost SR

For all patients who meet retreatment criteria at Week 16, Cycle 2 Bimatoprost SR administration will occur at Week 16.

For patients who do not meet retreatment criteria at Week 16, Cycle 2 Bimatoprost SR administration may occur at the investigator's discretion during an unscheduled visit after Week 16 and prior to the Month 12 visit based on the investigator's clinical judgment regarding the patient's IOP control and if the retreatment criteria are met. Note: beyond Week 16, Cycle 2 administration is not mandatory even if the retreatment criteria are met.

Patients who have received nonstudy IOP-lowering treatment (prohibited during the study except for pre- and post-SLT administration, Section 4.5.1) in only 1 eye will still attend administration visits regardless of whether the eye receiving additional medication is the Bimatoprost SR eye or the SLT eye. If the eye treated with additional nonstudy IOP lowering medication is the Bimatoprost SR eye, the eye will receive Sham Bimatoprost SR administrations at the administration visits. If the eye treated with additional nonstudy IOP lowering medication is the SLT eye, that eye will continue to receive Sham Bimatoprost SR administrations. Patients who have been treated with nonstudy IOP-lowering medication in both eyes will not attend the administration day visits, nor will they attend the Day 2, Day 4 (phone call), and Week 2 (phone call) visits following an administration. Patients who have received nonstudy IOP-lowering medication in one or both eyes will be followed for the duration of the study through the Month 24/Exit visit.

Retreatment of an eligible implanted eye is permitted if the following criteria are met in that eye:

- IOP > 17 mm Hg
- There is no evidence of any of the following:

- Significant corneal findings related to presence of the implant (including corneal edema, peripherally adjacent to the implant location and/or central) at any visit
- Endothelial cell density less than 1800 cells/mm² by specular microscopy, confirmed at 2 consecutive visits on separate days
- Persistent and progressive corneal endothelial cell density decrease $\geq 15\%$ from baseline confirmed at 2 consecutive visits on separate days (scheduled or unscheduled)

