| Amendment 6 | 
 • For patients who do not meet retreatment criteria at Week 16, the second administration of Bim SR 10 µg may be performed at the investigator's discretion during an unscheduled visit after Week 16 and prior to the Month 12 visit if the retreatment criteria are met. (Note that for all patients who were enrolled and reached the Week 16 visit prior to implementation of Amendment 6, retreatment with Bim SR was fixed at Week 16). |

To mask the patient to the treatment assigned to each eye, on Day 1 a Sham SLT procedure will be performed in the eye that will receive Bim SR administrations (hereafter referred to as the Bim SR eye). Similarly, a sham, needleless Bim SR administration (hereafter referred to as the Sham Bim SR administration and involves touching the eye at the area of insertion with a needleless applicator that does not deliver an implant into the anterior chamber) will be performed on the SLT-treated eye (hereafter referred to as the SLT eye) at the Bim SR administration visits.

Due to the paired-eye design of the study, the experimental units for treatment effects are individual eyes of each patient. Therefore, data summaries will primarily be done at eye level by randomized treatment (Bim SR and SLT). Where appropriate, data summaries at patient level will be provided.

Table 4-2 Treatment Schedule by Eye

| Treatment Visit | Bim SR Eye | SLT Eye |
|---|------------|-------------|
| SLT administration (Day 1) | Sham SLT | 360° SLT |
| Bim SR Cycle 1 administration (Day 4) | Bim SR | Sham Bim SR |
| Bim SR Cycle 2 administration (Week 16) ^a | Bim SR | Sham Bim SR |

SLT = selective laser trabeculoplasty; SR = sustained release

^a Cycle 2 administration of Bim SR is performed at Week 16 for all patients who meet retreatment criteria. For those patients not meeting retreatment criteria at Week 16, Cycle 2 may be performed at the investigator's discretion during an unscheduled visit after Week 16 and prior to the Month 12 visit if the retreatment criteria are met.

Three database locks will be performed:

- 1) when all patients treated with Bim SR 10 µg have completed the Week 24 visit or have prematurely discontinued before the Week 24 visit (referred to as the primary DBL);

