10.2.2 Time to Initial Use of Non-study IOP-lowering Treatment

Time to the initial use of non-study IOP-lowering treatment from the Date of the First Treatment as defined below will be analyzed using Kaplan-Meier (KM) method with graphical displays:

- Time to initial use of non-study IOP-lowering treatment = (Date of initial use of non-study IOP-lowering treatment – Date of the First Treatment) +1,

where the Date of the First Treatment for SLT is the SLT Treatment date (Day 1), and the Date of First Treatment for Bim SR 10 µg is Bim SR 10 µg administration date (Day 4).

Additionally, for Bim SR 10 µg, the time to non-study IOP-lowering treatment from the second injection will be summarized:

- Time to initial use of non-study IOP-lowering treatment from the second Bim SR 10 µg administration = (Date of initial use of non-study IOP-lowering treatment after the second Bim SR 10 µg implant – Date of the second Bim SR 10 µg administration) +1

In the calculation of time to initial use of non-study IOP-lowering treatment, if a patient did not use any non-study IOP-lowering treatment in an eye, then the event (initial use of non-study IOP-lowering treatment) time will be censored at the study exit date or the last visit date if the study exit date is not available.

In the calculation for the time to the event of non-study IOP-lowering treatment from the second Bim SR 10 µg administration, patients with at least two Bim SR 10 µg administrations will be used, and the event will be censored at the last available visit date or exit date if the patients did not use any non-study IOP-lowering treatment.

10.2.3 Percentage of Bim SR and SLT Eyes Achieving ≥ 20% Reduction by Visit

Number and percent of eyes that have achieved a ≥ 20% reduction in IOP at each post-baseline visit will be summarized by treatment.

10.2.4 IOP Changes from Baseline at Weeks 8, 15, and 20

IOP values at Week 8, 15 and 20 and the changes from baseline will be descriptively summarized for Bim SR 10 µg and SLT at each timepoint for the ITT population.

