12.0 SUBGROUP ANALYSES

Subgroup analyses will be conducted for patients who received the Bim SR 10 μ g administration under the flexible dosing regimen as specified in the protocol amendment 6 regardless of the visit at which patients received the second Bim SR 10 μ g administration. It will include patients enrolled under amendment 6 or patients re-consented to amendment 6 before receiving the second Bim SR 10 μ g administration. Otherwise, patients will be classified in the fixed dosing regimen subgroup.

In addition, subgroup analysis by the disease diagnosis, open-angle glaucoma (OAG) or ocular hypertension (OHT) at screening, will be performed on IOP data.

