12.2 TIME TO SECOND BIM SR ADMINISTRATION

For patients who received 2 Bim SR 10 μ g administrations under the flexible dosing regimen, the time from the first to the second administration will be analyzed using Kaplan-Meier (KM) method with graphical displays:

- Time to the second administration of Bim SR= (Date of the second administration of Bim SR 10 µg – Date of the First Bim SR 10 µg) +1.

In the calculation, if a patient did not receive the second Bim SR by Month 12 as specified in the study protocol, then the patient will be censored at Month 12 unless the patient withdrew early or received non-study IOP treatment prior to Month 12 visit which ever occurred first.

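### SAP 12.2 limits the Kaplan-Meier analysis of time to second implant to patients who received it, which contradicts its own censoring rule and takes the curve to 100%

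*SAP*

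**What the plan says.** **Population.** The analysis in SAP 12.2 is introduced with "For patients who received 2 Bim SR 10" µg administrations under the flexible regimen. The time analysed runs from the first implant to the second, plus one day.

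**Censoring.** The same section then covers a patient with no second implant by Month 12: "then the patient will be censored at Month 12 unless the patient withdrew early or received non-study IOP treatment prior to Month 12 visit", whichever came first.

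**Parent subgroup.** SAP 12.0 defines who belongs to the flexible regimen: "It will include patients enrolled under amendment 6 or patients re-consented to amendment 6 before receiving the second" implant. Membership depends on enrolment or re-consent under Amendment 6. Having had a second implant is not a condition.

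**Retreatment rule.** Protocol 5.9.1.5 gives the second implant at Week 16 to patients who meet the criteria, which include IOP above 17 mm Hg. Other patients may receive it later, before the Month 12 visit, at the investigator's discretion. After Week 16 it is not obligatory even when the criteria are met. Protocol section 8 expressly provides for patients who never have a second administration.

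**The concern.** A time-to-event analysis needs everyone at risk of the event, including those who never have it. SAP 12.2 selects patients on having had the event and then gives a censoring rule for those who did not. The two sentences cannot both be applied to the same patients.

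This section is the SAP's only analysis dedicated to when patients receive a second implant under the regimen that Amendment 6 introduced. A reader will take from it how many patients needed retreatment and how long they went before it. With the population as written, the display answers neither question. It drops exactly those patients in whom one implant was enough, in whom retreatment was ruled out, or who were given other treatment instead.

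**Working it through.** SAP 12.2 states no figure, so there is none to reproduce. The check is first logical, then a short calculation.

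**Step 1. Set the sentences side by side.**
- Stated set: flexible-regimen patients with two implants. Each has a second-implant date, so each has an event time.
- Censored group: patients with no second implant by Month 12.
- Protocol 5.9.1.5 allows the second implant only before the Month 12 visit. A patient treated per protocol therefore cannot be in both groups, and no such patient in the stated set is censored.

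**Step 2. Product-limit estimate.** S(t) is the product of (1 − d/n) over event times up to t, with d events among n at risk.
- Stated set: m patients, m events, no censoring. The product reduces to (m − events so far)/m, which is 0 after the last event. So 1 − S = 100% for any m.
- All N flexible-regimen patients with a first implant, none censored before Month 12: 1 − S at Month 12 = m/N, the true proportion retreated.

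**Step 3. Numbers.** Take N = 100 hypothetical patients and assume the share retreated. The last column assumes 10 non-recipients censored at random times before Month 12. It comes from one simulated set per row and is approximate.

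| Assumed share retreated by Month 12 | Population as written | All flexible patients, no early censoring | All flexible patients, 10% censored early |
|---|---|---|---|
| 30% | 100% | 30% | about 32% |
| 50% | 100% | 50% | about 54% |
| 67% | 100% | 67% | about 71% |
| 80% | 100% | 80% | about 87% |

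The 100% column needs no assumption about rates. The others show only how far it could lie from the truth.

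**Step 4. Is a large group without a second implant plausible?** The documents give one indication. In the phase 1/2 study, "at least 33% of patients had not received rescue or a second Bimatoprost SR treatment by Month 12" (Protocol 1.2.3). If that held here, at most 100% − 33% = 67% could have had a second implant by Month 12. That study's retreatment rule is not given and may differ, so this is not an estimate for this trial.

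**Step 5. The median.** Its shift depends on an assumption about timing. Suppose half of second implants fall at Week 16 and the rest evenly over Weeks 17 to 51.
- Recipients only: the median lies at Week 16 to 17 for any share retreated, because the assumption puts it there.
- All patients, 60% retreated: 30% have the event at Week 16, and a further 20 of the remaining 30 points are needed, so 17 + 34 × 20/30 = Week 39.7.
- All patients, 80% retreated: 17 + 34 × 10/40 = Week 25.5.
- All patients, 40% retreated: the median is not reached.

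Other timings give other answers. With 40% of recipients treated at Week 16, the recipients-only median is 17 + 34 × 0.1/0.6 = Week 22.7. With 80% retreated and 65% of those at Week 16, 0.80 × 0.65 = 52% of all patients have the event at Week 16, and both medians are Week 16.

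**Step 6. The eye in the censoring clause.** The clause names no eye, and only the Bim SR eye can have the event. If the eye given non-study medication "is the Bimatoprost SR eye, the eye will receive Sham Bimatoprost SR administrations at the administration visits" (Protocol 5.9.1.5), so the event is ruled out. If only the SLT eye is treated, "the contralateral eye that does not require nonstudy topical IOP-lowering medication will maintain the same treatment regimen assigned at randomization" (Protocol 4.5.2), and the event remains possible. For protocol-compliant patients this has no effect under the population as written, since none of them is censored. With the population corrected, take a true 60%, the Step 5 timing and no Bim SR-eye treatment. Assume SLT-eye treatment in 5%, 15% or 30% of patients, evenly over Weeks 4 to 51. Simulation gives 60.7%, 62.2% or 64.8% if treatment of either eye censors non-recipients, and 60.0% if only the Bim SR eye counts.

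**The case against.** The strongest reply is that the intent is clear. A rule for patients without a second implant makes sense only if they are in the analysis, and SAP 12.0 defines the subgroup without requiring one. SAP 10.2.2 correctly restricts to patients with two implants when it measures time from the second implant, so the wording in 12.2 looks like a drafting slip. This stands as an account of intent. It does not remove the contradiction: 12.2 never names the wider population, and whoever programs the display must set aside one of its two sentences. Nor does the remark in SAP 12.0 that subgroup membership is regardless of the visit of the second implant settle it, because the next sentence there defines membership by Amendment 6 alone.

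It can also be said that for recipients only, the interval shown is correct for recipients. That is true, but it is not the time to second implant for patients managed under the flexible regimen.

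A reader might infer more than the documents support:
- **That the censoring rule can apply to no one.** A patient given the second implant after Month 12, against the protocol, would be in the set and could be censored at Month 12. The 100% result is therefore for protocol-compliant patients.
- **That the unnamed eye is a second defect.** It has no practical effect under the literal population. Under the intended one, the SAP's convention answers it: SAP 4.0, after Table 4-1, says "the experimental units for treatment effects are individual eyes of each patient", SAP 10.2.2 speaks of the case "if a patient did not use any non-study IOP-lowering treatment in an eye", and SAP 17.1 treats data as missing eye by eye. A clarification is enough.
- **That the phase 1/2 rates or the medians above measure the error here.** The rates may not transfer, and the medians follow from the assumed timing.
- **That Kaplan-Meier itself is wrong because treatment of the Bim SR eye precludes the event.** Reporting a cumulative incidence with that treatment as a competing event would be a choice of estimand, not a correction.

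**Conclusion.** The point holds as a contradiction within SAP 12.2 that, followed as written, gives a misleading display. For patients treated per protocol the curve ends at 100% whatever the true retreatment rate, and patients who went without a second implant are excluded. That conclusion rests only on the section's own wording and the protocol's Month 12 limit. How far 100% lies from the true proportion cannot be derived from the documents; for assumed true values of 30% to 80%, the gap is 70 to 20 percentage points.

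Severity is minor. The analysis is a descriptive, single-group subgroup summary with no test attached. The noninferiority analysis, the superiority test and the other secondary efficacy results do not use it.

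**What to change.** In SAP 12.2, replace the population clause so that the analysis covers all flexible-regimen patients, as defined in SAP 12.0, who received the first Bim SR 10 µg implant. Keep the censoring rule as it is. In the same edit, state that censoring at non-study IOP-lowering treatment refers to the Bim SR eye and that treatment confined to the SLT eye does not censor.

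The cost is two wording changes. Implant dates and dates of non-study treatment by eye are already needed for SAP 10.2.2, so no new data field or additional output is required.

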12.3 ECL ANALYSES BY FIXED AND FLEXIBLE ADMINISTRATION

Analyses of time to ECL events and exposure-adjusted ECL rate as well as the number and percentage of patients by various thresholds as described in Section 11.3.5 will be performed separately for the subgroups of patients treated under the fixed and flexible administration regimens.

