- 2) when all patients treated with Bim SR 10 µg have completed the Month 12 visit or have exited the study prior to Month 12 (referred to as the Month 12 DBL). To provide sufficient safety follow-up data after the repeat administrations, the second database lock will occur when all patients have completed a minimum of 3 months of follow-up after the second administration or reached Month 12 without the need for the second administration; and
- 3) when all patients treated with Bim SR 10 µg have completed the Month 24 visit or have prematurely discontinued before Month 24 (referred to as the final DBL).

Analyses will be performed on unmasked data after each lock. The analysis based on the primary database lock will be considered as the primary analysis of the study. The analysis plan will support each of DBLs, but some analyses will be reduced for the final DBL (e.g, the primary efficacy analysis will not be re-produced at the final DBL).

Additional unmasked analyses based on accumulated data may be conducted after the initial Week 24 DBL (primary DBL) to support health authority submissions (e.g, 120 Day Safety Update and responses to questions). These analyses will be consisted of available data that are deemed suitable for regulatory submissions, although may not be of the quality standard used for formal, prespecified database locks.

Schedule of visits and procedures to be performed on randomized patients are presented in [Table 4-3](#) to [Table 4-7](#).

| Visit | Screening | | Baseline ^b | Day 1 (SLT Administration) | Day 2 Phone Call ^c |
|---|---------------|--|-----------------------|-------------------------------|----------------------------------|
| Visit Windows | Up to 28 days | | Up to 3 days | | |
| Pachymetry: (may be done any time after gonioscopy) | OU | | | | |
| Intraocular Pressure Hour 2 and Hour 8 (selected sites/patients^b) | | | OU | | |
| Pupil Dilation (may perform post-dilation eye exams in any order) | OU | | OU | | |
| Dilated Ophthalmoscopy | OU | | OU | | |
| Optic Disc Examination | OU | | OU | | |
| Determination of Eligibility | X | | X | X | |
| Contact Interactive Response System ^m | X | | X | X | |
| Treatment and/or Sham Administration | | | | X | |

IOP = intraocular pressure; OU = both eyes; SLT = selective laser trabeculoplasty; X = do procedure; Hour 0 = 08:00 ± 1 hour; Hour 2 = Hour 0 + 2 hours (± 30 min); Hour 8 = Hour 0 + 8 hours (± 30 min)

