11.3.5 Specular Microscopy

Endothelial cell density average (cells/mm²) will be assessed using specular microscopy performed on the central cornea of each eye at Screening, Week 4, Week 12, Week 24, Week 40, Week 52, Month 16, Month 20, and Month 24/Exit. Baseline endothelial cell density (measured at Screening), raw values, and change from baseline as well as percent changes from baseline will be summarized descriptively by visit and analysis cycle for each eye.

The number and percentage of patients will be tabulated by various thresholds (including but not limited to endothelial cell count change; e.g. $\geq 10\%$ gain, $\geq 10\%$ loss, $\geq 15\%$ loss, etc.) for the percent change from baseline at each visit and at the last visit (i.e., last visit assessment). Overall summary during the entire study and within analysis cycle will be summarized based on the greatest decrease from baseline.

Kaplan-Meier Analysis for Time to ECL Event

To further investigate the endothelial cell loss (ECL), time to event analyses will be performed on the ECL event using Kaplan-Meier (KM) method with graphical displays. The ECL event is defined as post-baseline percent loss in central corneal endothelial cell density (CECD) meeting a specified threshold. The analyses of ECL events will be performed for threshold values of $\geq 15\%$ and $\geq 20\%$. For each threshold value, *First Observed ECL* and *First Confirmed ECL* are defined as following:

1. *First Observed ECL*: The first *observed* ECL meeting the threshold is considered the initial ECL event.
2. *First Confirmed ECL*:

The first *confirmed* ECL event is defined as the first of two ECLs meeting the same threshold at two consecutive visits (scheduled or unscheduled) with CECD assessment done on different days.

- ✓ For discontinued or completed patients, if the first ECL event meeting the threshold occurs at the patient’s final CECD assessment before discontinuing/exiting the study, the loss will be counted as a confirmed loss at that date.
- ✓ For analyses performed prior to the final database lock, if a patient is continuing in the study and the first ECL meeting the threshold occurs at the

most recent CECD assessment visit before data cutoff, the loss will NOT be counted as a confirmed loss.

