The KM analyses will be performed for each of the first *confirmed* ECL and the first *observed* ECL. Compelling evidence of intra-eye variability of CECD has been observed in global, well-controlled, randomized, multicenter studies despite methodological measures in place to control for CECD variability. Therefore, the key analysis for Time to ECL Event will be based on the confirmed ECL values. For each analysis, Time (days) is calculated as follows:

- Time to the First *Confirmed* ECL event = (Date of the First *Confirmed* ECL event – Date of the First Study Treatment) + 1,
- Time to the First *Observed* ECL event = (Date of the First *Observed* ECL event – Date of the First Study Treatment) + 1,

where the Date of First Study Treatment is the first date of Bimatoprost SR 10 µg or SLT administration. For eyes that did not have any observed ECL events, time to the first ECL event will be right-censored at the last available CECD assessment date.

For each scheduled visit, the tabulation will display the number of eyes at risk, cumulative number of eyes with events, and the cumulative probability of event and the associated 95% confidence interval.

Exposure Adjusted Analysis for ECL Rate

Additionally, to take into account the differences in follow up time, an exposure-adjusted analysis for ECL rate over the entire study period will be performed by treatment for Bimatoprost SR 10 µg and SLT treated eyes. Exposure time will be calculated for each treated eye. For eyes that experienced an ECL event during the study, exposure time is the number of days from the first study treatment administration to the date when the first ECL event occurred. For eyes without an ECL event, exposure time is the number of days from the first study treatment administration to the last assessment for CECD. Exposure time in person-years is calculated as (exposure time in days)/365.25. Exposure adjusted ECL rate will be calculated per 100 person-years as:

- $100 \times (\text{number of eyes that experienced the ECL event}) / \text{total exposure time in person-years for the treatment group}$.

Listings for patients with $\geq 20\%$ CECD loss at any visit will be provided.

Coefficient of Variation Average (CV_{AVE}): Coefficient of variation average of raw data and changes from baseline will be summarized descriptively by visit and analysis cycle for each eye.

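### At the Week 24 and Month 12 locks, worst-ever endothelial loss percentages by regimen rise with the fixed subgroup's longer follow-up, and the exposure-adjusted rate does not reliably correct for it

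*SAP*

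**What the plan says.** **Subgroups (SAP 12.0).** Of the flexible group the SAP says: "It will include patients enrolled under amendment 6 or patients re-consented to amendment 6 before receiving the second" implant. For the rest: "Otherwise, patients will be classified in the fixed dosing regimen subgroup". Table 4-1 (SAP 4.0) adds that for patients who "were enrolled and reached the Week 16 visit prior to implementation of Amendment 6, retreatment with Bim SR was fixed at Week 16".

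**Locks (SAP 4.0, 14.0).** The first lock waits for the last 10 µg patient's Week 24 visit, the second for Month 12 (and at least 3 months after any second implant), the third for Month 24. "Analyses will be performed on unmasked data after each lock", and each lock has its own study report.

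**ECL analyses (SAP 11.3.5).** Specular readings fall at Weeks 4, 12, 24, 40 and 52 and Months 16, 20 and 24. Threshold percentages are tabulated at each visit and at the last visit. In addition, "Overall summary during the entire study and within analysis cycle will be summarized based on the greatest decrease from baseline". Kaplan-Meier analyses cover first observed and first confirmed loss. Confirmed loss is the key version, because the SAP acknowledges variability of cell density readings within an eye. Finally, "to take into account the differences in follow up time, an exposure-adjusted analysis for ECL rate over the entire study period will be performed". Its denominator is calendar time to the first event or the last reading.

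**By regimen (SAP 12.3).** The time-to-event, rate and threshold analyses "will be performed separately for the subgroups of patients treated under the fixed and flexible administration regimens".

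**The concern.** The first two locks occur when the last patients reach a visit, so patients who entered earlier have been followed longer by then. Those are mostly the fixed-regimen patients. A worst-ever percentage grows with the number of readings, so the two subgroups would differ at identical risk. The rate is the SAP's remedy for unequal follow-up, but it divides by calendar time, whereas loss can be seen only at a reading and readings become sparser.

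At stake is how two study reports present corneal safety under fixed against IOP-triggered re-implantation. Someone comparing the two columns could take a follow-up artefact for an effect of regimen.

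**Working it through.** The documents give no ECL percentage, rate, subgroup size or Amendment 6 date, so there is no plan figure to reproduce. The check asks what SAP 11.3.5 would report for two **identical** groups that differ only in follow-up.

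**1. Reading density.** Cycle 1 target days in SAP Table 17-3 are 25, 81, 165, 277, 361, 477, 597 and 717.
- To Week 24: 3 readings, 3/(165/365.25) = 6.6 per eye-year
- To Week 52: 5 readings, 5/(361/365.25) = 5.1
- To Month 24: 8 readings, 8/(717/365.25) = 4.1

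**2. Worst-ever percentage.** An eye's greatest decrease over 5 readings cannot be smaller than over the first 3. The percentage therefore cannot fall as follow-up lengthens, whatever the noise or hazard.

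**3. Rate, observed loss.** Let p be the chance of a false crossing per reading (assumed; not in the documents). The percentage after K readings is 1 − (1−p)^K. Exposure is the sum of each gap between readings times the fraction of eyes still event-free. For p = 2%:
- Week 24: 1 − 0.98³ = 5.9%. Exposure 25 + 56×0.98 + 84×0.98² = 160.6 days = 0.440 years. Rate 5.88/0.440 = 13.4 per 100 person-years.
- Week 52: 1 − 0.98⁵ = 9.6%. Exposure 160.6 + 112×0.98³ + 84×0.98⁴ = 343.4 days = 0.940 years. Rate 9.61/0.940 = 10.2.

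The same calculation under other assumptions:

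| Assumption, identical regimens | Week 24: %, rate | Week 52: %, rate | Rate ratio |
|---|---|---|---|
| Noise only, p = 1% | 3.0, 6.7 | 4.9, 5.1 | 1.31 |
| Noise only, p = 2% | 5.9, 13.4 | 9.6, 10.2 | 1.31 |
| Noise only, p = 5% | 14.3, 33.8 | 22.6, 26.0 | 1.30 |
| p = 2% plus true hazard 3%/year | 7.1, 16.3 | 12.2, 13.2 | 1.24 |
| No noise, constant hazard 5%/year | 2.2, 4.98 | 4.8, 4.97 | 1.00 |
| No noise, rising hazard (Weibull shape 2, 10% at 24 months) | 0.5, 1.2 | 2.5, 2.6 | 0.46 |

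Thinning of readings alone does not move the rate (fifth row). Noise per reading or a changing hazard does.

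**4. Reading-error model.** Simulated eyes with independent error on baseline and on each reading; event = first observed loss of at least 15%. The SD is an assumption.
- No true loss, SD 5%: 3.1% and 6.9 at Week 24; 4.7% and 4.9 at Week 52 (rate ratio 1.41).
- No true loss, SD 7%: 12.7% and 30.0; 18.1% and 20.5 (ratio 1.46).
- True loss 3% per year, SD 5% to 7%: percentage ratio 0.48 to 0.61, rate ratio 1.04 to 1.26.
- True loss 3% per year, SD 4%: rates 2.1 and 2.6 (ratio about 0.8).

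For Week 52 against Month 24, the extreme case at the second lock, true loss of 3% per year and SD 5% to 7% give rate ratios of 0.82 to 1.10.

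**5. Confirmed loss.** Before the final lock, an ongoing patient's first crossing at the latest reading is not counted. That leaves 2 confirmable readings for an eye followed to Week 24 and 4 for one followed to Week 52.
- SD 5% to 7%, no true loss: rates 0.4 to 3.8 at Week 24 and 0.4 to 3.1 at Week 52, a gap of at most 0.7.
- With 3% per year true loss: rate ratio 0.72 to 0.98.
- Constant true hazard 5%/year, no noise: 1.1% and 2.5 at Week 24; 3.7% and 3.8 at Week 52.

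**6. Time-aligned analyses.** By-visit percentages and Kaplan-Meier probabilities at a given visit compare eyes at the same time, so unequal length of follow-up does not distort them. One edge remains for confirmed loss: a Week 24 crossing can be confirmed later in a longer-followed eye, but not in an ongoing eye whose latest reading is Week 24.

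**The case against.** The strongest case on the other side has five parts.

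- **The rate is not distorted by construction.** Correct: with a constant hazard and no noise it is flat (4.98 against 4.97). A distortion needs noise or a changing hazard. The SAP acknowledges the noise without giving its size, and gradual loss toward a threshold implies a rising hazard.
- **Confirmed loss is the key definition.** Correct for the time-to-event analysis, and it shrinks the noise-driven gaps to little. But the rate paragraph does not say which event it uses, and confirmed percentages still rise with follow-up.
- **Time-aligned tables already exist.** Correct. SAP 11.3.5 tabulates percentages by visit and Kaplan-Meier probabilities with numbers at risk, and 12.3 repeats them by regimen. What remains concerns the worst-ever percentages and the rate.
- **No fixed-against-flexible test is planned.** Correct. The results are reported separately, and the rate is defined for Bim SR against SLT eyes. Fellow eyes share the reading schedule, so the SLT eye is a useful reference within each subgroup. Even so, separate tables by regimen invite comparison, and no contrast using the SLT eye is specified.
- **The follow-up gap is unknown.** Correct. Patients who entered before Amendment 6 and re-consented count as flexible, and those who left early without re-consenting count as fixed. The wait after second implants can also lengthen flexible follow-up at the second lock. Setting one group at Week 24 and the other at Week 52 shows the mechanism; it does not forecast the size.

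**Conclusion.** The point holds for the Week 24 and Month 12 locks and for two summaries. The by-regimen worst-ever percentages rise with follow-up at identical risk, which needs only that fixed patients have, on average, more follow-up. The exposure-adjusted rate does not reliably remove the difference. For observed loss of at least 15% and assumed reading SDs of 4% to 7%, the Week 24 to Week 52 rate ratio is about 0.8 to 1.5, and the documents do not fix its direction.

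A reader might infer more than the documents support:
- that the rate must differ between regimens: it need not, under a constant hazard without noise;
- that percentage and rate will point in opposite directions: this happens for noise-driven observed loss, but is weak or absent for confirmed loss;
- that only Kaplan-Meier estimates are usable: by-visit percentages are aligned in time too;
- that the final lock is affected: planned follow-up is equal there.

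This is an inexpensive improvement to descriptive safety tables. It does not touch the primary analysis or the overall safety summaries.

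**What to change.** In SAP 12.3, for the first two locks:
- Compute the by-regimen greatest-decrease percentages and the exposure-adjusted rate on a common window: through the Week 24 reading at the first lock and the Week 52 reading at the second. Count the window from first treatment, because Table 17-3 restarts its visit windows at the second implant.
- State whether the rate uses observed or confirmed events, and apply the confirmation rule only to readings inside the window.
- Say that fixed against flexible is to be read from the planned Kaplan-Meier and by-visit tables at those visits.
- Keep the all-follow-up figures by regimen for the final lock, or label them as not comparable at the earlier ones.

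The cost is a few sentences and one truncation step in existing programs, with no new data. Later readings of fixed patients drop out of the early regimen tables but stay in the overall safety tables.
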